## **7. Criteria for Exclusion of Subjects:**

**Exclusion criteria:** Subjects meeting any of the exclusion criteria at baseline will be excluded from study participation.

1. Known congenital or chromosomal anomalies
2. Congenital heart disease (other than PDA, PFO or ASD)
3. Multiple pregnancy

## **8. Sources of Research Material:**

We are going to use the discarded placenta/Umbilical Cord unit and as the resource of PUCB samples and left-over blood sample after CBC is done as blood from infant.

## **9. Recruitment Methods and Consenting Process:**

### *Recruitment*

All eligible infants born at UTMB Galveston will be recruited in the study. We expect 50 - 60% success in the recruitment after accounting for exclusion criteria and timing of delivery. If the infant is born after hours, the research team may not be available to collect the PUCB sample. We admit around 80 infants/year who are <34 weeks' gestation. We hope to recruit our desired sample size (n=63) in 18 months.

### *Consenting process*

In the current research protocol, we will collect PUCB after birth, which is considered as discarded tissue. We will not collect any blood or any other body fluid from the subjects. This will be less than minimal risk to the subjects. Therefore, consent is not required.

## **10. Potential Risks:**

There is no potential risk to the subjects since PUCB will be collected after birth and placenta and umbilical cord is considered discarded. There will not be any direct interaction with the subjects.

## **11. Subject Safety and Data Monitoring:**

Subject's safety will not be affected as we will be collecting the blood samples from the placenta/umbilical cord after birth which is discarded material. All the data will be collected and saved in a password protected computer. Only PI and research team will have access to the computer and the data.

## **12. Procedures to Maintain Confidentiality:**

No information regarding the study or the clinical data will be released to any unauthorized third party without the prior written approval of the principal investigator. The investigators are committed to maintaining the confidentiality of the subjects through the proper use and disclosure of patients' personal health information (PHI). Study records may be made available for internal compliance reviews and quality assurance representatives.

## **13. Potential Benefits:**

There will be no direct benefit to the subjects. But the results of this study may help us to find out if PUCB could be utilized to evaluate EOS in VLBW infants. The results of this study will provide understanding of the utility of PUBC samples to evaluate EOS in VLBW preterm infants. Moreover, this alternative modality of blood analysis could contribute to the prevention of early hemodynamic instability and early blood transfusion in a very high-risk population of VLBW preterm infants. Furthermore, an additional test for sepsis screening as CRP and IL 6, might improve the accuracy for EOS evaluation, and may avoid or prevent unnecessary and prolong antibiotic use in ELBW infants.

## **14. Biostatistics:**

Statistical analyses will be performed using SPSS 25 for Windows (SPSS Inc., Chicago, IL, USA). Demographic and clinical characteristics will be compared using the non-parametric Mann-Whitney U test, and the results will be presented as medians (range). Categorical variables will be compared using the linear-by-linear association Chi-squared test and will be presented as percentages (%). Receiver operator curve (ROC) analysis will be employed to display the relationship between sensitivity and false positive (FP) rate (1-specificity) and to select the best cut-off value for umbilical cord IL-6 and CRP to predict EOS. Data will be as adjusted by gestational age at delivery, administration of prenatal corticosteroids and antibiotics. Differences will be considered statistically significant at a confidence level of  $p < 0.05$  with two-sided alternative hypotheses

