## **3. Concise Summary of Project:**

Hypothesis: Placental/umbilical cord blood can be used to do early onset sepsis evaluation in low birth weight infants.

Objective: To compare placental/umbilical cord blood and blood from the infant in the evaluation of EOS in VLBW infants.

Specific Aim 1: To compare blood culture, CBC and I/T ratio results of blood from the infant and placental/umbilical cord blood (PUCB).

Objective: All VLBW infants receive empirical broad-spectrum antibiotics after collecting blood for CBC, I/T ratio, and blood culture. We will compare the results of PUCB and blood from the infants, especially comparing white cell count, band count, I/T ratio and if the blood culture is positive or negative. If the blood culture is positive, then we will find out if the micro-organism is the same or not.

Specific Aim 2: To evaluate the role of adding IL-6 and CRP in the evaluation of EOS in VLBW infants.

Objective: We will collect 1 mL of PUCB which will be centrifuged at -40C and serum will be stored at -80 degrees. We will use ELISA to measure IL-6 and CRP. A combination of IL-6 and CRP has been shown to be very helpful in the diagnosis of EOS in VLBW infants. We will also calculate sensitivity, specificity, negative predictive and positive predictive values of IL-6 and CRP individually, as well as, a combination of IL-6 and CRP in the diagnosis of EOS in VLBW infants. We will also find out the duration of antibiotics used in all subjects and find out from IL-6 and CRP data if the antibiotic use was warranted. In future, this may be very useful information in deciding antibiotic duration which will help in avoiding side effects of the unnecessary use of broad-spectrum antibiotics. At present, in our NICU, IL-6 and CRP are not part of EOS evaluation in VLBW infants.

Clinical team will be blinded to the PUCB sepsis evaluation results. In the present study, IL-6 and CRP will not be used clinically but only for research purpose to find out if the addition of IL-6 and CRP help in the management of EOS in VLBW infants.

All VLBW infants get CBC done at admission before starting antibiotics as part of EOS work up. After CBC is done, left over blood sample is saved in the hematology laboratory for 24 hours. We will collect the left-over sample and collect serum after centrifugation. The serum will be saved at -800C for future measurement of IL-6 and CRP. We will compare IL-6 and CRP from infant and PUCB.

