#### *Placenta/Umbilical Cord blood (PUCB):*

In the current research project, we want to use PUCB to do sepsis evaluation in VLBW infants. There is approximately 15 – 20 mL/kg blood in the placenta and umbilical cord. That means in VLBW infants (<34 w) there will be approximately 15 – 20 mL blood in the placenta and umbilical cord which is fetal blood hence it can be utilized to do EOS sepsis evaluation. This

will save blood in VLBW infants. As blood in PUCB is nothing but fetal blood. There is a misconception that fetal and maternal blood is mixed in the placenta. Actually, there is no mixing of maternal and fetal blood in the placenta. After birth, the placenta and umbilical cord are discarded along with the blood inside. We want to utilize fetal blood in the placenta/umbilical cord for the evaluation of EOS in VLBW infants.

The current research project will evaluate the utility of PUCB to assess early onset sepsis (EOS) in VLBW infants (<34 weeks). This study will not affect the management of the infants at all. The lab tests will be done in blocks and hence the results will not be available in real time. The clinical management of infants will be decided by the neonatal team taking care of the infants. The neonatologists will continue to treat infants as per the NICU protocol.

We will compare blood culture, CBC, and I/T ratio results from the infant and PUCB. We will calculate the sensitivity, specificity, positive and negative predictive value of these tests in the evaluation of EOS.

During hospital stay, all VLBW infants get CBC done immediately after birth. After CBC is done, the left-over sample is stored in the hematology laboratory for 24 hours. After 24 hours, this blood sample is discarded. We will collect left over blood from the hematology laboratory to extract serum by centrifuging the blood sample. The serum will be stored at -80°C for future measurements of CRP and IL-6. We will also compare CRP and IL-6 levels in placenta/umbilical cord blood and discarded infant blood. Additionally, we will evaluate the role of adding IL-6 and CRP in the evaluation of EOS in VLBW infants.

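### Cord blood is compared with the same infant's blood, but Section 14 names no paired test and no agreement estimate for that comparison

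*Combined protocol and SAP*

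**What the plan says.** The objective in Section 3 (Concise Summary of Project) is "To compare placental/umbilical cord blood and blood from the infant in the evaluation of EOS in VLBW infants". Specific Aim 1 covers culture and blood count results, "especially comparing white cell count, band count, I/T ratio and if the blood culture is positive or negative", and adds for culture: "If the blood culture is positive, then we will find out if the micro-organism is the same or not". The subsection on PUCB extends the comparison to the biomarkers: "We will also compare CRP and IL-6 levels in placenta/umbilical cord blood and discarded infant blood". The Power analysis subsection describes one cohort. Section 8 (Sources of Research Material) names the placenta/cord unit and the infant's left-over CBC sample as the two sources. Each infant therefore supplies both members of a pair.

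Section 14 is the only section that names statistical tests. It says:
- for continuous data, "Demographic and clinical characteristics will be compared using the non-parametric Mann-Whitney U test";
- for categorical data, "Categorical variables will be compared using the linear-by-linear association Chi-squared test";
- ROC analysis "to select the best cut-off value for umbilical cord IL-6 and CRP to predict EOS".

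It adds an adjustment for gestational age, prenatal corticosteroids and antibiotics, and a two-sided 0.05 significance rule. Outside Section 14, the PUCB subsection says of culture, CBC and I/T ratio: "We will calculate the sensitivity, specificity, positive and negative predictive value of these tests in the evaluation of EOS". The Clinical Data Collection subsection extends those measures to CRP and IL-6.

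**The concern.** The hypothesis is that PUCB can serve for the sepsis evaluation. For Aim 1, a direct way to support it is to show how closely the PUCB result matches the infant's own result, infant by infant. No method in Section 14 estimates that.

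Two things follow. First, a reader who applies the categorical sentence as written to paired culture or I/T results will either ignore the pairing (comparing two percentages) or test association (cross-table). Neither measures agreement. Second, the only decision rule is p < 0.05 for a difference, and the plan does not say how a non-significant difference will be read. It could be taken as evidence that the samples are interchangeable. Choosing the method after the data are seen would also leave room for a favourable choice.

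**Working it through.** **1. What is compared, and which method is assigned**

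| Result | Place in the plan | Paired or agreement method in Section 14 |
|---|---|---|
| Culture | Aim 1 | None. The categorical sentence may or may not be meant to apply |
| WBC, band count, I/T ratio | Aim 1 | None. Mann-Whitney is given to demographic and clinical characteristics |
| CRP, IL-6 levels | Compared as a secondary matter | None. ROC addresses cord values against EOS |

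**2. Does the sample size supply a method?** The stated 63 can be reproduced as a one-sided test of a single correlation against zero: ((1.645 + 1.645)/atanh 0.4)² + 3 = (3.290/0.4236)² + 3 = 63.3. The r = 0.4 comes from correlations of CRP with other biomarkers, not of PUCB with infant blood. Section 14 lists no correlation analysis, and correlation is not agreement. So it does not fill the gap.

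**3. What the named categorical test does with pairs**

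The inputs are assumptions, not figures from the documents: 63 complete pairs and an infant result positive in 20 of 63 (32%). Section 2 says I/T is raised in a quarter to half of infants without sepsis, and using that range for the whole cohort is part of the assumption. Cells are both positive / PUCB only / infant only / both negative. For a 2×2 table the linear-by-linear statistic is (N − 1)/N times Pearson's chi-squared, on 1 df.

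*Example A: 20/8/0/35*
- Two percentages, 28/63 against 20/63 (N = 126): Pearson 126 × (28×43 − 35×20)² / (63×63×48×78) = 2.154; × 125/126 = 2.137; p = 0.14.
- Exact McNemar, 8 discordant pairs all one way: 2 × 0.5⁸ = 0.008.
- Cross-table: 63 × (20×35 − 8×0)² / (28×35×20×43) = 36.63; × 62/63 = 36.05; p = 2e-9.
- Overall agreement 55/63 = 87%. Expected by chance (28×20 + 35×43)/63² = 0.520. Kappa = (0.873 − 0.520)/(1 − 0.520) = 0.74.

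Agreement is fairly good, with a one-sided excess of PUCB positives. The two-percentages use misses that excess, and the cross-table says only that the results are associated.

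*Example B: 10/10/10/33*
- Two percentages, 20/63 against 20/63: statistic 0, p = 1.00.
- Cross-table: 63 × (10×33 − 10×10)² / (20×43×20×43) = 4.506; × 62/63 = 4.435; p = 0.035.
- Overall agreement 43/63 = 68%. Expected by chance (20×20 + 43×43)/63² = 0.567. Kappa = (0.683 − 0.567)/(1 − 0.567) = 0.27. Positive agreement 2×10/(2×10 + 10 + 10) = 50%.
- Exact McNemar also gives p = 1.00.

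One use shows no difference and the other shows a significant association, while half of the positives fail to match. McNemar does not reveal this either, so agreement estimates must lead and paired tests can only support.

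**4. Limits of the data for culture.** Exact McNemar with d discordant pairs all one way has p = 2 × 0.5^d: 0.0625 for d = 5 and 0.031 for d = 6. Fewer than 6 discordant pairs can never give p < 0.05. If all k infant-positive cultures are matched, the exact lower 95% limit for infant-referenced positive agreement is 0.025^(1/k): 2.5% for k = 1, 16% for k = 2 and 29% for k = 3. The documents give no expected number of positive cultures.

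**5. Precision for continuous results with 63 pairs**, in units of the SD of the within-infant differences:
- bias: t(0.975, 62)/√63 = 1.999/7.937 = ±0.25;
- each 95% limit of agreement: 1.96 × √(3/63) = ±0.43.

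**The case against.** Several points on the other side have force.

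- A reader might infer that the plan prescribes Mann-Whitney for the paired laboratory values. It does not: that sentence covers demographic and clinical characteristics. The continuous pairs have no assigned method, which is an omission. Mann-Whitney is the only continuous comparison test named. It would be unsuitable if used by default, because it treats the pairs as independent.
- A reader might infer that neither concordance nor accuracy is planned. That is also wrong. The organism match is planned, and sensitivity, specificity and predictive values are planned for culture, CBC, I/T, CRP and IL-6. These address culture concordance and prediction of EOS. They do not say how far the two samples' values differ within an infant.
- The six results do not carry equal weight. Aim 1 concerns culture, CBC and I/T. CRP and IL-6 belong to Aim 2, their measurement is under Sub-Study Procedures, and their paired comparison is an addition. For them the cut-off is to be chosen on cord values, so an offset from infant levels would not by itself make cord values unusable. The agreement argument is strong for Aim 1 and weaker for the biomarkers.
- The categorical sentence may have been meant for baseline characteristics only. Then the test is not misapplied, but culture and dichotomised I/T also have no comparison method.
- It is tempting to treat the infant culture as the truth. Sections 1 and 2 describe blood culture as insensitive, so the documents do not support counting every PUCB-only positive as a PUCB error.

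These points narrow the concern. None supplies a paired or agreement method.

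**Conclusion.** The concern holds. Section 14 has no paired test and no agreement estimate for the comparison that forms the main objective, chiefly culture, WBC, band count and I/T ratio, and secondarily CRP and IL-6. This rests on the documents alone.

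The numerical examples are illustrations. They assume 63 complete pairs, 32% positivity and chosen cell counts, and they apply only if the unrestricted categorical sentence is used on paired results. Under those assumptions the named test can miss a one-sided difference (p = 0.14 against exact McNemar p = 0.008), and can be significant (p = 0.035) when kappa is 0.27. No figure is claimed for the continuous results, because the plan assigns them no test. Patient care is not affected, since the protocol states that the study does not alter management. The gap concerns the main objective and should be closed before the data are analysed.

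**What to change.** In Section 14:

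1. State that every PUCB-versus-infant comparison is paired within infant.
2. For WBC, band count and I/T ratio, and secondarily CRP and IL-6, report the within-infant bias and 95% limits of agreement with confidence intervals. Use the log scale for skewed positive values, or a non-parametric version where there are zeros or values below assay limits. Give Wilcoxon signed-rank as support.
3. For culture and dichotomised I/T, report the paired 2×2 table with overall, positive and negative agreement and confidence intervals. Use reference-neutral measures, or show the infant-referenced version as well. Add the organism match for culture. Make exact McNemar secondary, and note that it needs at least 6 discordant pairs to reach p < 0.05.
4. Restrict Mann-Whitney and linear-by-linear chi-squared to comparisons between independent groups of infants.
5. State that a non-significant difference is not evidence of agreement, and give the expected precision (about ±0.25 SD on the bias and ±0.43 SD on each limit with 63 pairs).

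The cost is plan wording and a little more analysis work. Data collection, sample size and software are unchanged. If interchangeability is to be claimed, the investigators would also need to set acceptable limits before looking at the data. No value is proposed here.

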#### *Power analysis:*

In order to do a power analysis to determine sample size, an estimate of effect size was based upon the Rashawn et al (30) study which found significant correlations of CRP with other biomarkers.

In G\*Power (31) the following was used:

- Effect size of  $r=.4$
- Alpha=.05
- Power (1-alpha)=.95
- Yielding a sample size of 63

To accomplish this project, a cohort of preterm infants will be recruited from the infants admitted to the NICU at UTMB, Galveston. We routinely admit around 80 infants/year who are <34 weeks' gestation. We expect to recruit about 50 – 60% VLBW infants born in UTMB, Galveston in the current study. Therefore, we hope to recruit our desired sample size (n=63) in about 18 months.

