#### *Clinical Data Collection:*

We will use electronic medical records to collect medical data from mother's antenatal, delivery and post-delivery information and detailed medical information of the infants. Data derived from blood test analysis in placenta/umbilical blood cord and blood from the infants will be used to assess the accuracy of placenta/umbilical blood cord samples. We will also find out specificity, sensitivity, positive and negative predictive values of CBC, I/T ratio, blood culture, CRP and IL-6 in the evaluation of EOS in ELBW infants. All data will be de-identified but the clinical data will be linked to the discarded samples.

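### The linear-by-linear chi-squared is set for every categorical variable, so results for unordered variables with three or more levels depend on arbitrary level codes

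*Combined protocol and SAP*

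**What the plan says.** Section 14 gives one rule for categorical data: "Categorical variables will be compared using the linear-by-linear association Chi-squared test and will be presented as percentages". It does not limit the rule to ordered categories, fix any coding of levels, or name a Pearson or exact alternative. No other section adds one.

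The neighbouring rule in Section 14, "Demographic and clinical characteristics will be compared using the non-parametric Mann-Whitney U test", is reported as medians and ranges, so it does not provide for nominal characteristics either. Tests are to be at the 0.05 level "with two-sided alternative hypotheses".

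The data source is broad. Under Clinical Data Collection in Section 3: "We will use electronic medical records to collect medical data from mother's antenatal, delivery and post-delivery information and detailed medical information of the infants". No variable list follows. The categorical items that the documents do name are mostly two-level:
- culture result, in Section 3 ("if the blood culture is positive or negative"), and whether the organism is the same in both samples;
- in Section 14, "administration of prenatal corticosteroids and antibiotics", named as adjustment factors.

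Species of organism, identified under PUCB culture in Section 4, is the one clearly unordered item with several levels.

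**The concern.** The linear-by-linear statistic measures the linear correlation between scores given to the rows and scores given to the columns. When the levels have a natural order, the scores carry meaning. When they do not, the scores are whatever numbers the database assigned. Two analysts with the same data and different code lists would then report different p-values.

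The single degree of freedom is spent on one direction, which is arbitrary here, so a real difference concentrated in a level that happens to be coded in the middle can be missed. Because the plan fixes no coding, there is also room to choose one after seeing the data. What is at stake is how the comparisons of characteristics between infants with and without EOS can be interpreted.

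**Working it through.** **Inputs.** N = 63 comes from Section 3, Power analysis ("Yielding a sample size of 63"). The number of EOS cases and all table counts are assumptions, because the documents give none.

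**The plan's own figure.** With r = 0.4, alpha 0.05 and the printed "Power (1-alpha)=.95", the exact test of a correlation gives N = 63 one-sided (power 0.952) and N = 75 two-sided. So 63 reproduces one-sided only. That is a separate matter; here 63 only sets the size of the tables.

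**Formula.** M² = (N − 1)r², referred to chi-squared on 1 df, where r is the Pearson correlation of the scores. With two groups of size n0 and n1, r² = (n0·n1/N)·d²/SS. Here d is the difference in mean score and SS is the total sum of squares of the scores about their mean.

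**Three unordered levels, 58 infants without EOS (24/18/16) and 5 with EOS (0/5/0).** n0·n1/N = 58 × 5/63 = 4.603.

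| Codes for the three levels | Mean, EOS | Mean, no EOS | SS | M² | p |
|---|---|---|---|---|---|
| 1, 2, 3 | 2 | 108/58 = 1.862 | 260 − 118²/63 = 38.98 | 62 × 4.603 × 0.138²/38.98 = 0.14 | 0.71 |
| 2, 3, 1 | 3 | 118/58 = 2.034 | 319 − 133²/63 = 38.22 | 62 × 4.603 × 0.966²/38.22 = 6.96 | 0.0083 |
| 1, 3, 2 | 3 | 110/58 = 1.897 | 295 − 125²/63 = 46.98 | 62 × 4.603 × 1.103²/46.98 = 7.40 | 0.0065 |

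Reversing a coding changes nothing, so these are the only three values. The Fisher-Freeman-Halton exact p, by full enumeration, is 0.0054 under any numbering.

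**Four unordered levels (22/16/14/6 against 0/4/0/1).** The 24 codings give 12 distinct p-values, from 0.0097 to 0.99. Five are below 0.05 and seven above. The exact p is 0.035 under any numbering.

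**Less extreme tables, groups of 20 and 43.**
- 10/3/7 against 11/22/10: p = 0.548, 0.029 or 0.009 by coding; Pearson p (2 df) is 0.022 throughout.
- 8/2/7/3 against 9/19/6/9: p from 0.002 to 0.73; Pearson p (3 df) is 0.020 throughout.

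**Two levels.** Any two codes are a linear transformation of any other two, so r² cannot change, and M² is the Pearson chi-squared times (N − 1)/N. For 6/14 against 25/18: 4.325 × 62/63 = 4.256, p = 0.039 under every coding.

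**Size of the two-level test.** This was enumerated in full for N = 63, 2, 3, 5 or 7 EOS cases, and a characteristic present in 5–50% of infants. With 3 to 7 cases the true type I error is 3.1–6.4%. It reaches 8.6–9.0% only with 2 cases and a prevalence of 5–10%. Fisher's exact test in the same settings has a true size between 0 and 3.6%.

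**The case against.** **The test is not invalid.** A reader might infer that the plan yields wrong p-values or an inflated false-positive rate for nominal variables. That goes too far. Under independence, any scores fixed in advance give a statistic that is approximately chi-squared on 1 df. The defects are arbitrariness and weak power against non-trend differences. A chance finding becomes more likely only if the coding is chosen after the data are seen, which the plan leaves open but does not propose.

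**The affected variables are not listed.** A reader might suppose that ethnicity or the reason for preterm delivery will be compared. Neither appears in the documents. Organism species is nominal, but it exists only for positive cultures, and Section 3 uses it solely as same or different, so it is not a factor for comparing infants with and without EOS.

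**The main tables are extreme.** They place all or nearly all of the EOS cases in one level. This is fair, but the more balanced tables also cross 0.05 on renumbering alone.

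**For two-level variables the existing test is reasonable.** This stands. Its size is near nominal in most settings examined, and replacing it everywhere with Fisher's test would lose power where numbering does no harm.

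**The aims do not rest on this test.** This also stands: the ROC curves and the sensitivity, specificity and predictive values do not use it.

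What survives is that Section 14 states a general rule, and for unordered variables with three or more levels that rule has no defensible score and no alternative.

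**Conclusion.** The point holds in a narrow form and is minor. For an unordered variable with three or more levels compared between independent groups, the rule in Section 14 gives a p-value that depends on arbitrary codes. With N = 63 and 5 assumed EOS cases, the range is 0.0065 to 0.71 for three levels and 0.010 to 0.99 for four. The tables are illustrations and do not forecast the trial's data. The dependence on coding is a property of the statistic and does not rest on them; how often it will matter depends on which nominal variables are analysed, and the documents do not say. The reach is limited to descriptive and baseline comparisons.

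**What to change.** Replace the sentence on categorical variables in Section 14 with:

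> For comparisons between independent groups, unordered categorical variables with three or more levels will be compared with the Fisher-Freeman-Halton exact test. The linear-by-linear test will be used only for ordered or two-level variables, with exact or mid-p values where expected counts are small. This does not apply to paired cord-versus-infant results.

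The last clause is needed because the cord and infant samples come from the same infant. A test for independent groups would not suit them, and their analysis should be specified separately.

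The cost is one sentence, with no new data, visits or infants. The downside is slight conservatism of exact tests in sparse tables. Keeping the linear-by-linear test for two-level variables, with mid-p as an option, avoids most of the loss that a blanket switch to Fisher's test would bring.

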## 2.1 *C-Reactive Protein (CRP)*

CRP is one of the most sensitive acute-phase reactants for inflammation. CRP is synthesized by the liver. The CRP response frequently precedes clinical symptoms of sepsis. CRP acts within the humoral immune system, particularly in the detection and clearance of bacterial microorganisms. CRP level increases within 6-18 hours after a stimulus and peaks 8-60 hours later (13). The fetus and newborn synthesize CRP; its level is not affected by gestational age, and CRP does not cross the trans-placental passage of maternal CRP (14).

CRP elevations are nonspecific and may be useful for the detection of systemic inflammatory processes; to assess treatment of bacterial infections with antibiotics. In neonates, CRP has been shown to be more sensitive and specific in diagnosing sepsis than the more commonly used CBC indices (total neutrophil count and I/T ratio) (15). Joram et al found that CRP (cut-off point of 5 mg/dl) measured in umbilical cord blood has a sensitivity, specificity, positive and negative predictive values are respectively 50%, 97%, 67% and 94%. Besides, the same study found that the positive and negative likelihood ratios were 16.7 and 0.5 for CRP (28).

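### A 'best' cord IL-6 and CRP cut-off is to be picked by ROC in 63 infants not selected for sepsis, with no expected number of EOS cases and no rule for few or none

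*Combined protocol and SAP*

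**What the plan says.** Section 14 (Biostatistics) states that "Receiver operator curve (ROC) analysis will be employed", in part "to select the best cut-off value for umbilical cord IL-6 and CRP to predict EOS". It does not define 'best', and it says nothing of confidence intervals or of what happens when cases are scarce. Section 3 adds accuracy measures: Specific Aim 2 promises sensitivity, specificity and both predictive values for IL-6, CRP and their combination, and the paragraphs on placenta/umbilical cord blood and on clinical data collection promise the same for CBC, I/T ratio and culture.

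The sample size is in the Power analysis part of Section 3: an effect size of r = .4, taken from a study "which found significant correlations of CRP with other biomarkers", with alpha .05 and "Power (1-alpha)=.95", "Yielding a sample size of 63". In Section 9, "All eligible infants born at UTMB Galveston will be recruited in the study". Eligibility (Sections 6 and 7) is birth before 34 weeks at the centre, less anomalies, congenital heart disease and multiple pregnancy. Suspected sepsis is not a criterion.

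The only definition of EOS is in Section 1, and it requires a positive culture before 72 hours of age. Section 1 gives a relative incidence for preterm against term infants but no absolute rate.

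**The concern.** A ROC curve, a selected cut-off and a sensitivity all need infants with EOS. A sample size derived from a correlation between biomarkers does not control how many such infants there will be. Followed as written, the plan has two weak outcomes. With no EOS cases, the ROC part of Aim 2 cannot be computed. With one to three, the ROC can be computed and will return a best cut-off, but that value is set by where one to three infants happen to fall among about sixty others.

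The second outcome matters more, because it looks like a result. Section 3 says the IL-6 and CRP information may in future help decide antibiotic duration, and Section 13 returns to that hope. A cut-off produced by chance could be carried forward as evidence.

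**Working it through.** **The plan's own figure.** Inputs from the Power analysis: r = 0.4, alpha 0.05, power 0.95. The exact bivariate normal test of zero correlation, one-sided, gives N = 63 (power 0.952). Fisher's z gives ((1.645 + 1.645)/atanh 0.4)² + 3 = 63.3. So 63 reproduces, but only one-sided. Section 14 tests "with two-sided alternative hypotheses", for which the exact N is 75 and the power at 63 is 0.911. That mismatch is a separate matter, since neither number says anything about EOS cases.

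**Number of cases.** The rate p is my assumption, shown as a range. The top of the range is back-calculated from the cord CRP study in Section 2.1, whose sensitivity, specificity, "positive and negative predictive values are respectively 50%, 97%, 67% and 94" per cent. From sensitivity 0.50, specificity 0.97 and PPV 0.67, the odds of infection are (0.67/0.33) × (0.03/0.50) = 0.122, so prevalence is 0.122/1.122 = 10.9%. This returns NPV = 0.97 × 0.891/(0.97 × 0.891 + 0.50 × 0.109) = 94%, as stated. With cases distributed as Binomial(63, p):

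| Assumed rate | Expected (63p) | P(0 cases) = (1−p)^63 | P(3 or fewer) | P(4 or fewer) |
|---|---|---|---|---|
| 1% | 0.6 | 53% | 99.6% | over 99.9% |
| 2% | 1.3 | 28% | 96% | 99% |
| 5% | 3.2 | 4% | 61% | 79% |
| 11% | 6.9 | under 0.1% | 7% | 16% |

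**What a ROC with few cases returns.** Take 'best' as the maximum Youden index J = sensitivity + specificity − 1 (my assumption) and a marker unrelated to EOS. With one case, the best cut-off is that infant's own value, sensitivity is 100%, and J = 1 − (non-cases above it)/62. J is at least 0.5 when no more than 31 of the 62 non-cases lie above, which has probability 32/63 = 51%. For more cases, I simulated random ranks of k cases among 63. The exact lower 95% limit when all k cases are detected is 0.025^(1/k).

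| EOS cases k | P(J ≥ 0.5), useless marker | Lower limit for sensitivity, k/k detected |
|---|---|---|
| 1 | 51% | 2.5% |
| 2 | 27% | 16% |
| 3 | 19% | 29% |
| 5 | 7% | 48% |
| 7 | 3% | 59% |

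**The case against.** The strongest reply is that the documents give no absolute EOS rate, and the one figure that can be extracted from them, about 11%, makes neither bad outcome likely. This stands. A reader might infer that the ROC step fails at any plausible incidence, and the documents do not support that. At 11%, about seven cases are expected, none is very unlikely, and three or fewer has a 7% chance. What remains there is imprecision: a lower limit of 59% even for 7/7. The 11% also comes from another cohort, whose definition of infection is not given here.

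The case definition is less settled than it looks. Section 1 is introductory, Section 14 does not restate the definition, and studies cited in Sections 2.2 and 2.3 also count clinical sepsis. A wider definition would raise the count, but the plan does not adopt one.

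A reader might also treat IL-6 and CRP as two independent chances of a false success, giving 76%, 47% and 34% with 1, 2 and 3 cases (1 − (1 − P)²). Independence conflicts with Section 2.2, where IL-6 drives CRP synthesis, and with the r = .4 in the Power analysis. At a correlation of 0.4, simulation gives about 69%, 43% and 31%. I do not rely on either set. Nor are the single-marker figures distinct from the optimism of a fitted cut-off: they measure that optimism when cases are few.

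Finally, enrolled infants are not put at risk. Section 3 keeps the clinical team blind to the cord results, bars clinical use of IL-6 and CRP, and speaks of antibiotic duration only as a future possibility. The harm is confined to how the results may be read later.

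**Conclusion.** The concern holds in conditional form. Without any assumption about incidence, the documents show a commitment to select a cut-off and report accuracy, a sample size unrelated to case numbers, enrolment not selected on sepsis, and neither an expected case count nor a rule for few cases. How likely this is to matter depends on the rate and on the culture-positive definition. At 5% or below, three or fewer cases is the likelier outcome, and a cut-off chosen from so few can make an uninformative marker look useful. Near 11%, a ROC is very likely to be estimable but sensitivity stays poorly determined. The Youden figures further assume that criterion and the 0.5 threshold. The gap should be closed. It does not undermine the comparison of cord and infant values for CBC, I/T ratio, IL-6 and CRP.

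**What to change.** No extra infants are needed.

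- **Section 3, Power analysis:** state the expected number of EOS cases among 63 infants over an assumed incidence range, and the case definition used.
- **Section 14, status and reporting:** call the EOS accuracy analyses (IL-6, CRP, their combination, CBC, I/T ratio and culture) exploratory. Give the number of EOS cases and an exact 95% interval beside every sensitivity and predictive value. Recommend no cut-off for use.
- **Section 14, minimum case number:** fix it before marker values are linked to EOS status. The value is the sponsor's choice, and 5 is only an example. Below it, run no ROC, select no cut-off, list individual IL-6 and CRP values by EOS status, and rest conclusions on the cord-versus-infant comparison of CBC, I/T ratio, IL-6 and CRP. That comparison needs no EOS cases. The comparison of culture results and organisms in Specific Aim 1 does need positive cultures, so it cannot serve as the fallback.

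The cost is a few sentences and a more modest Aim 2, which may deliver no cut-off. With a minimum of 5, the chance of falling short is 99%, 79% and 16% at assumed rates of 2%, 5% and 11% (the P(4 or fewer) column above).
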